4.4.5 Digital CT/MRI/PET Imaging Data Submission Using TRIAD

TRIAD is the American College of Radiology's (ACR) image exchange application. TRIAD provides sites participating in clinical trials a secure method to transmit DICOM RT and other objects. TRIAD anonymizes and validates the images as they are transferred.

TRIAD Access Requirements:

- Site physics staff who will submit images through TRIAD will need to be registered with the Cancer Therapy Evaluation Program (CTEP) and have a valid and active CTEP Identity and Access Management (IAM) account, and be registered as an A, AP, NPIVR or IVR. Please refer to CTEP Registration Procedures of the protocol for instructions on how to request a CTEP-IAM account.
- To submit images, site staff must hold the TRIAD Site User role on an NCTN or ETCTN roster. Individuals requiring a TRIAD Site User role should contact the person holding a primary role at the site for their affiliated NCTN or ETCTN roster.
- All individuals on the Imaging and Radiation Oncology Core provider roster have access to TRIAD, and may submit images for credentialing purposes, or for enrollments to which the provider is linked in OPEN.

TRIAD Installations:

When a user applies for a CTEP-IAM account with the proper user role, he/she will need to have the TRIAD application installed on his/her workstation to be able to submit images. TRIAD installation

documentation can be found by following this link
<https://triadinstall.acr.org/triadclient/>

This process can be done in parallel to obtaining your CTEP-IAM account username and password and RCR registration.

If you have any questions regarding this information, please send an e-mail to the TRIAD Support mailbox at [contact] or [name].

4.5 Instructions for Patients who Do Not Start Assigned Protocol Treatment

If a patient does not receive any assigned protocol treatment, baseline and follow-up data will still be collected and must be submitted through Medidata Rave according to the schedule in the EA2142 Forms Completion Guidelines.

Rev. 2/17

5. Treatment Plan

NOTE: No therapies (investigational or commercial agents) other than those described below may be administered with the intent to treat the patient's malignancy. No other investigational treatment may be given for any purpose while on study.

Rev. Add3

NOTE: Patients whom have received prior somatostatin analogue therapy are permitted to stay on it if the treating physician feels that they are deriving clinical benefit from it for hormone mediated symptoms.

NOTE: An assessment of drug-drug interactions between patient's medication list and the assigned treatment should be conducted using updated package inserts prior to initiation of treatment.

All doses are based on actual body weight. If there is a < 10% change in weight, keep the doses the same. If there is a $\geq 10\%$ change in weight, a new dosing weight should be set and used for dose calculations. If the newly calculated weight results in no change to the dose (for oral agents only), the same dose may be used if felt to be indicated by the treating physician.

5.1 Administration Schedule

5.1.1 Capecitabine and Temozolomide —Arm A

Cycle = 28 days (+/- 2 days)

- Capecitabine 750 mg/m² by mouth every 12 hours (+/- 2 hours) on days 1-14
- Temozolomide 200mg/m² by mouth once daily on days 10-14

NOTE: Please refer to the Patient Pill Calendar in [Appendix III](#). Patients are required to return their completed Patient Pill Calendar at each clinic visit.

Premedication required: Ondansetron or an approved 5HT3 antagonist should be used as a premedication 30-60 minutes prior to temozolomide. Other anti-emetics, anxiolytics, and analgesics may be provided at physicians' discretion

Continue treatment until patient develops disease progression (as defined by Section [6.1.4](#)) or unacceptable toxicity

Patients will need to be asked about other drugs they are taking at home such as OTC products, herbal medicines, tea, or other prescribed drugs. Patients should record this information on their Pill Calendar

5.1.1.1 Arm A Treatment Notes

Monitor CBC and platelet count prior to drug administration.

- The calculated total daily capecitabine dose by body surface area (BSA) will be used and treatment should be administered according to the following table Only 500 mg tablets will be used:

Dose: 750 mg/m ² every 12 hours (or 1500 mg/m ² /day)		500 mg tabs	
Surface Area (m ²)	Total Daily Dose (mg)	# tabs in AM	# tabs in PM
1.2-1.5	2000	2	2
1.51-1.83	2500	3	2
1.84-2.16	3000	3	3
2.17-2.5	3500	4	3
2.51-2.83	4000	4	4

- Capecitabine should be taken morning and night, with at least 12 hours (+/- 2 hours) between each dose. Capecitabine pills should be swallowed with water within 30 minutes after a meal. Capecitabine pills may not be crushed. Capecitabine missed doses will not be made up and patients should not double-up on missed doses during treatment.
- The temozolomide dose will be capped at 400 mg daily. The calculated dose by BSA will be rounded to the closest mg amount permitted within the confines of available pill sizes. Temozolomide should be taken by mouth at night after fasting from solid food for two hours. Temozolomide capsules must not be crushed and must be administered whole. Temozolomide missed doses will not be made up and patients should not double-up on missed doses during treatment.

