5.1.2 Cisplatin (or Carboplatin) and Etoposide—Arm B

Cycle = 21 days (+/- 2 days)

CBC will be monitored prior to day 1 of drug administration.

Premedication with ondansetron (or other 5HT3 antagonist) and dexamethasone prior to each chemotherapy administration (days 1-3) is required. Additional antiemetics, analgesics and anxiolytics may be used per the discretion of the treating physician. Pre- and post-treatment hydration may be administered per institutional standards.

If the treating physician chooses to use Aprepitant, when given once daily for 14 days as a 100 mg capsule with an oral contraceptive containing 35 mcg of ethinyl estradiol and 1 mg of norethindrone, this decreased the AUC of ethinyl estradiol by 43% and decreased the AUC of norethindrone by 8%. Women of childbearing potential using pregnancy contraception that includes ethinyl estradiol should not receive Aprepitant for the treatment of nausea/delayed emesis. Patients may change to a different method of contraception if they wish to use Aprepitant.

- Cisplatin 25 mg/m² daily x 3 days (days 1-3) to be administered per institutional guidelines.

OR

- Carboplatin target AUC of 5 once on day 1 to be administered per institutional guidelines

AND

- Etoposide 100mg/m² daily x 3 days (days 1-3) to be administered per institutional guidelines.

Continue treatment until patient develops disease progression (as defined by Section [6.1.4](#)) or unacceptable toxicity.

NOTE: Treatment will be administered on an outpatient basis unless local institutional standard practice requires inpatient administration.

NOTE: CALVERT FORMULA FOR CARBOPLATIN DOSING:

Total Dose (mg) = (target AUC) x (GFR + 25)

For the purposes of this protocol, the GFR is considered to be equivalent to the creatinine clearance.

Round up any creatinine \leq 0.6 mg/dL, to 0.6 mg/dL

Glomerular Filtration Rate (GFR) Estimation: Calculated creatinine clearance of \geq 50 cc/min using the Cockcroft-Gault formula:

Males:
$$\frac{(140 - \text{Age in years}) \times \text{Actual Body Weight in kg}}{72 \times \text{Serum Creatinine (mg/dL)}}$$

Females: Estimated creatinine clearance for males x 0.85

With the Calvert formula, the total (final) dose of carboplatin is calculated in mg, not mg/m².

DO NOT exceed a dose of 150 mg per AUC or cap at 750 mg/AUC5.

NOTE: Choice of platinum agent will be per treating physician discretion. Once a platinum agent is picked, no changes are allowed.

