5.3 Dose Modifications

5.3.1 General

Dose reductions will be based on current dose. If dose reduction is required, reduction is permanent. Missed doses will not be made up. No dose escalation is permitted for any of the study drugs.

Dose will be modified for all drugs if there is $\geq 10\%$ change in patient's weight while on study. For oral agents, particularly capecitabine, a new dose calculation may result in the same number of pills to be administered due to rounding issues.

Doses will be determined according to (1) non-hematologic AEs during the previous cycle, as well as (2) the lowest ANC and platelet counts during that cycle.

Patients may receive **a maximum of two** dose reductions per agent. If a third reduction is required, the patient should discontinue all protocol treatment. However, for Arm A, patients may discontinue one agent due to toxicity and continue the other on-study.

If different percentages of dose reductions for a specific drug are required because of two different types of toxicities, the greater percentage dose reduction should be undertaken.

AEs determined to be unrelated to study treatment will not require dose reduction.

NOTE: If patients have been off study treatment ≥ 4 weeks of next planned cycle start date, patients must discontinue protocol treatment.

NOTE: Starting cycles early is prohibited due to safety purposes.

All toxicity grades below are described using the NCI Common Terminology Criteria for Adverse Events (CTCAE) version 4.0.

All appropriate treatment areas should have access to a copy of the CTCAE version 4.0. A copy of the CTCAE version 4.0 can be downloaded from the CTEP website (<http://ctep.cancer.gov>).

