5.3.2 Capecitabine Dose Modifications

Capecitabine will be initiated at 750 mg/m^2 orally twice daily $\times 14$ days on a 28-day treatment cycle. Dose should be calculated as a total daily dose of 1500 mg/m^2 , then divided into two doses.

For all capecitabine dose modifications, if the protocol indicated that the dose should be reduced for subsequent administrations, a reduction of at least 500 mg (of the total daily dose) should be implemented even if the calculation including the dose reduction results in the same number of pills as was originally administered (example: if treated originally at 2500 mg daily, only 2000 mg daily may be administered if a dose reduction was called for).

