5.3.3 Temozolomide Dose Modifications

- **Dose reductions:** For non-hematologic grade 3 and 4 AEs (except for nausea and vomiting as well as AEs unrelated to treatment) the dose should be reduced according to the Temozolomide Dose Level Table at the discretion of the investigator. Dose reductions for treatment day ANC and platelet counts should also be made according to the Dose Level Table below. Each dose reduction will be a 20% reduction from the prior level.
- **Discontinuation:** Also, except for nausea and vomiting, if any of the same non-hematologic grade 3 and 4 AEs that are at least possibly related to temozolomide recur after two reductions for that AE, then temozolomide will be stopped.

Temozolomide Dose Level Table	
Dose Level	Dose in mg/m ²
0	200
-1	160
-2	128

*Note this is a 20% dose reduction with each dose level.

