5.3.3.1 Hematologic Toxicity

ANC (/mm ³)		Platelets (/mm ³)	% of Planned Temozolomide
≥ 1500/mm ³	and	≥ 100,000/mm ³	100%
750-1499/mm ³	or	50,000-99,999/mm ³	Hold*
< 750/mm ³	or	< 50,000/mm ³	Hold**

* Upon recovery to ANC ≥ 1,500/mm³ and platelets to ≥ 100,000/mm³, the dose level -1 will be administered (160 mg/m²). Discontinue temozolomide dose if patients do not recover within ≤ 3 weeks. If patient was already receiving Temozolomide at the -1 dose level, reduce to the -2 dose (128 mg/m²).

** Upon recovery to ANC ≥ 1,500/mm³ and platelets to ≥ 100,000/mm³, the dose level -2 will be administered (128 mg/m²). Discontinue dose if patients do not recover within ≤ 3

weeks. If patient was already receiving Temozolomide at the -2 dose level, temozolomide should be discontinued.

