8.2.5 Dose Specifics

200 mg/m² by mouth once daily on days 10-14 (Arm A)

The temozolomide dose will be capped at 400 mg daily and is available as 5, 20, 100, 140, 180, or 150 mg capsules. The calculated dose by body surface area (BSA) will be rounded down to minimize the number of pills required.

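### The 400 mg temozolomide cap is not scaled at levels -1 and -2, so above BSA 2.0 the first reduction is less than the stated 20%, and at BSA 2.5 or more it is nil

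*Combined protocol and SAP*

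**What the plan says.** Section 5.1.1 starts temozolomide at 200 mg/m² once daily on days 10-14. Section 5.1.1.1 limits it: "The temozolomide dose will be capped at 400 mg daily". Section 8.2.5 repeats the limit ("The temozolomide dose will be capped at 400 mg daily and is available as" six capsule sizes, the smallest 5 mg). Neither place ties the cap to a dose level.

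The Temozolomide Dose Level Table in Section 5.3.3 lists 200, 160 and 128 mg/m² for levels 0, -1 and -2. The text above it says "Each dose reduction will be a 20% reduction from the prior level", and the footnote repeats the 20%. The same section sends reductions for ANC and platelet counts to that table. Section 5.3.3.1 then names the dose to give once counts recover:

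- ANC 750-1499 or platelets 50,000-99,999: "the dose level -1 will be administered (160 mg/m²").
- ANC below 750 or platelets below 50,000: "the dose level -2 will be administered (128 mg/m²").

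Section 5.3.1, which covers all study drugs, says "Dose reductions will be based on current dose" and allows at most two reductions per agent.

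**The concern.** A mg/m² ladder with 20% steps delivers 20% steps in milligrams only while the dose is proportional to BSA. A flat cap breaks that proportionality at level 0. Because the cap does not shrink with the level, a capped patient moves from 400 mg to 160 mg/m² times BSA, and the larger the patient, the smaller the cut.

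What is at stake is re-treatment after myelosuppression. A reduction meant to lower exposure by a fifth may lower it by much less, or not at all, yet it still counts toward the limit of two. The protocol expects patients of this size: the capecitabine tablet table in Section 5.1.1.1 runs to BSA 2.83, and its top two rows (2.17-2.5 and 2.51-2.83) lie entirely above the point where the temozolomide cap binds.

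**Working it through.** **Inputs.** Starting dose 200 mg/m² (5.1.1); cap 400 mg daily (5.1.1.1, 8.2.5); levels 160 and 128 mg/m² (5.3.3, 5.3.3.1); five dosing days per cycle (days 10-14).

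**The plan's own figures.** 200 × 0.8 = 160 and 160 × 0.8 = 128, so the table reproduces exactly. Two steps give 1 - 0.8 × 0.8 = 36%.

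**Where the cap binds.** At level 0, 400/200 = BSA 2.0. At level -1, 400/160 = BSA 2.5. At level -2, 400/128 = BSA 3.125. Up to BSA 2.0 nothing goes wrong: at 1.8, 360 mg falls to 288 mg, a 20% cut.

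**Dose given under the table.** Dose = min(400, level × BSA). Cut = 1 - (new dose)/(old dose).

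| BSA | Level 0 (mg) | Level -1 (mg) | Level -2 (mg) | Cut 0 to -1 | Cut 0 to -2 | Cut -1 to -2 |
|---|---|---|---|---|---|---|
| 2.0 | 400 | 320.0 | 256.0 | 20% | 36% | 20% |
| 2.1 | 400 | 336.0 | 268.8 | 16% | 32.8% | 20% |
| 2.2 | 400 | 352.0 | 281.6 | 12% | 29.6% | 20% |
| 2.3 | 400 | 368.0 | 294.4 | 8% | 26.4% | 20% |
| 2.4 | 400 | 384.0 | 307.2 | 4% | 23.2% | 20% |
| 2.5 | 400 | 400.0 | 320.0 | 0% | 20% | 20% |
| 2.6 | 400 | 400.0 | 332.8 | 0% | 16.8% | 16.8% |

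**Gap from a true 20% cut.** A 20% cut from 400 mg is 320 mg. The level -1 dose exceeds this by 16 mg a day at BSA 2.1, 32 mg at 2.2 and 80 mg at 2.5 or more. Over five days that is 80, 160 and 400 mg per course.

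**Capsule rounding.** Assume 5 mg steps, the smallest capsule; Section 8.2.5 does not say how coarse rounding down may be. Level -1 is then 335 mg at BSA 2.1 (16.25% cut) and 350 mg at 2.2 (12.5%). Rounding to the closest step (5.1.1.1) restores 320 mg only below about BSA 2.02; rounding down (8.2.5) does so only up to about 2.03.

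**Other capped or coarse doses.** The Arm B carboplatin limit is set per unit of AUC ("DO NOT exceed a dose of 150 mg per AUC or cap at 750 mg/AUC5"), so it moves from 150 × 5 = 750 mg to 150 × 4 = 600 mg at level -1, a full 20%. For capecitabine, "a reduction of at least 500 mg (of the total daily dose) should be implemented" even when the calculation returns the same tablets. Temozolomide has no corresponding provision.

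**The case against.** The strongest reply is that the table means what it says. Section 5.3.3 sends count-driven reductions to a table in mg/m², 5.3.3.1 names 160 and 128 mg/m², and 5.3.3.2 makes the table binding for non-hematologic reductions. On that view level -1 is a BSA-adjusted ceiling. A patient with BSA 2.2 on 400 mg is already at 400/2.2 = 182 mg/m², and one with BSA 2.5 is at 160 mg/m², so a smaller further step is coherent. This stands as a reading of the text. It does not remove the clinical difficulty: the patient became cytopenic on 400 mg, and the prescribed response may be 400 mg again.

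A reader might go further and infer that the protocol contradicts itself, with 5.3.1 requiring 320 mg and 5.3.3.1 requiring 160 mg/m². The documents do not support that. Section 5.3.1 gives a basis and no percentage. The 20% comes from 5.3.3, where it is measured from the prior level, and levels are in mg/m². The phrase in 5.3.1 is naturally read as saying that reductions compound from the present level. The specific temozolomide sections therefore largely govern, and what remains is a cap that nobody scaled.

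The comparators also deserve care. The carboplatin limit scales because the Calvert formula is proportional to AUC, and the capecitabine rule addresses 500 mg tablets. They show what an effective reduction looks like, but not that the authors recognized this problem and overlooked it for one drug.

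Finally, other safeguards apply. Temozolomide waits for full count recovery and stops if that takes more than three weeks. A further episode at level -1 leads to level -2. Capecitabine is held and cut 20% for ANC below 1500 or platelets below 100,000 (5.3.2.1). Growth factors are allowed (5.4.10), and non-hematologic temozolomide reductions are at the investigator's discretion. These limit the harm but do not restore the missing reduction.

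**Conclusion.** The point holds as an unaddressed cap. Under the governing mg/m² levels, every patient with BSA above 2.0 who steps from level 0 to -1 has a calculated cut below 20%, shrinking to nothing at BSA 2.5. The direct step to level -2 also falls short of 36%, although it still removes at least 20% up to BSA 2.5. The step from -1 to -2 is a full 20% for BSA 2.0-2.5.

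The figures assume the 400 mg limit applies unchanged at every level, which is all the text provides. The documents give neither a BSA distribution nor a reduction rate, so the number of patients affected cannot be estimated; it is probably small in an arm of about 40 (80 planned over two arms). The shortfall is modest just above BSA 2.0 and matters most from about 2.3 upward. This is a minor safety correction that leaves the primary comparison, alpha and power untouched.

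**What to change.** Add a column to the Temozolomide Dose Level Table with a daily maximum for each level: 400 mg at level 0, 320 mg at level -1, 256 mg at level -2. Refer to it from Sections 5.1.1.1 and 8.2.5. Every step then lowers the capped patient's calculated dose by 20%, before capsule rounding.

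The cost is one column in an amendment and lower dose intensity in large patients after toxicity. At level -2, 256 mg is 256/2.2 = 116 mg/m² at BSA 2.2 and 256/2.5 = 102 mg/m² at BSA 2.5, against the nominal 128. If the team prefers to keep the uncapped mg/m² levels for these patients, one sentence should say so and acknowledge that the first step may then be smaller than 20% or absent. Neither option changes the sample size or the analysis.

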5.1.2 Cisplatin (or Carboplatin) and Etoposide—Arm B

Cycle = 21 days (+/- 2 days)

CBC will be monitored prior to day 1 of drug administration.

Premedication with ondansetron (or other 5HT3 antagonist) and dexamethasone prior to each chemotherapy administration (days 1-3) is required. Additional antiemetics, analgesics and anxiolytics may be used per the discretion of the treating physician. Pre- and post-treatment hydration may be administered per institutional standards.

If the treating physician chooses to use Aprepitant, when given once daily for 14 days as a 100 mg capsule with an oral contraceptive containing 35 mcg of ethinyl estradiol and 1 mg of norethindrone, this decreased the AUC of ethinyl estradiol by 43% and decreased the AUC of norethindrone by 8%. Women of childbearing potential using pregnancy contraception that includes ethinyl estradiol should not receive Aprepitant for the treatment of nausea/delayed emesis. Patients may change to a different method of contraception if they wish to use Aprepitant.

- Cisplatin 25 mg/m² daily x 3 days (days 1-3) to be administered per institutional guidelines.

OR

- Carboplatin target AUC of 5 once on day 1 to be administered per institutional guidelines

AND

- Etoposide 100mg/m² daily x 3 days (days 1-3) to be administered per institutional guidelines.

Continue treatment until patient develops disease progression (as defined by Section [6.1.4](#)) or unacceptable toxicity.

NOTE: Treatment will be administered on an outpatient basis unless local institutional standard practice requires inpatient administration.

NOTE: CALVERT FORMULA FOR CARBOPLATIN DOSING:

Total Dose (mg) = (target AUC) x (GFR + 25)

For the purposes of this protocol, the GFR is considered to be equivalent to the creatinine clearance.

Round up any creatinine \leq 0.6 mg/dL, to 0.6 mg/dL

Glomerular Filtration Rate (GFR) Estimation: Calculated creatinine clearance of \geq 50 cc/min using the Cockcroft-Gault formula:

Males:
$$\frac{(140 - \text{Age in years}) \times \text{Actual Body Weight in kg}}{72 \times \text{Serum Creatinine (mg/dL)}}$$

Females: Estimated creatinine clearance for males x 0.85

With the Calvert formula, the total (final) dose of carboplatin is calculated in mg, not mg/m².

DO NOT exceed a dose of 150 mg per AUC or cap at 750 mg/AUC5.

NOTE: Choice of platinum agent will be per treating physician discretion. Once a platinum agent is picked, no changes are allowed.

5.2 Adverse Event Reporting Requirements

Rev. Add3

NOTE: Starting April 1, 2018, all expedited adverse events reporting through CTEP-AERS are required to use CTCAE v5, however, this study will continue to utilize CTCAE v4 for routine adverse event reporting in Rave and dose modifications.

5.2.1 Purpose

Adverse event (AE) data collection and reporting, which are required as part of every clinical trial, are done to ensure the safety of the patients enrolled, as well as those who will enroll in future studies using similar agents.

- **Routine reporting:** Adverse events are reported in a routine manner at scheduled times during a trial using Medidata Rave.
- **Expedited reporting:** In addition to routine reporting, certain adverse events must be reported in an expedited manner for

timelier monitoring of patient safety and care. The following sections provide information and instructions regarding expedited adverse event reporting.

5.2.2 Terminology

- **Adverse Event (AE):** Any untoward medical occurrence associated with the use of a drug in humans, whether or not considered drug related. Therefore, an AE can be **ANY** unfavorable and unintended sign (including an abnormal laboratory finding), symptom, or disease temporally associated with the use of a medicinal product, whether or not considered related to the medicinal product.
- **Attribution:** An assessment of the relationship between the adverse event and the protocol treatment, using the following categories.

ATTRIBUTION	DESCRIPTION
Unrelated	The AE is clearly NOT related to treatment.
Unlikely	The AE is doubtfully related to treatment.
Possible	The AE may be related to treatment.
Probable	The AE is likely related to treatment.
Definite	The AE is clearly related to treatment.

- **CTCAE:** The NCI Common Terminology Criteria for Adverse Events provides a descriptive terminology that is to be utilized for AE reporting. A grade (severity) is provided for each AE term.
- **Expectedness:** Expected events are those that have been previously identified as resulting from administration of the agent. An adverse event is considered unexpected, for expedited reporting purposes, when either the type of event or the severity of the event is NOT listed in the protocol or drug package insert.

